4.5.3.2 Electrocardiograms

Twelve-lead electrocardiograms (ECGs) should be performed according to the schedule of assessments (see [Appendix 1](#)) and reviewed by the investigator or his or her designee. Whenever possible, the same machine should be used for each patient. To minimize variability, it is important that patients be in a resting position for ≥ 10 minutes prior to each ECG evaluation. Body position should be consistently maintained for each ECG evaluation to prevent changes in heart rate. Environmental distractions (e.g., television, radio, conversation) should be avoided during the pre-ECG resting period and during ECG recording. ECGs should be performed prior to receipt of study drug, any scheduled vital sign measurements, and blood draws. For safety monitoring purposes, the investigator or his or her designee must review, sign, and date all ECG tracings. Paper copies will be kept as part of the patient's permanent study file at the site. Digital recordings will be stored at study sites. ECG outcomes of "normal" or "abnormal" should be reported on the eCRF. New or worsened abnormalities should be recorded as AEs on the Adverse Event eCRF.

4.5.3.3 Chest X-Rays and Computed Tomography Scans

Posterior–anterior chest X-rays (or chest X-ray in accordance with local requirements) should be obtained at screening and, if normal, only if indicated thereafter. If chest X-ray is abnormal, it should be repeated at Month 1 and as indicated thereafter.

At screening, if a chest X-ray has been obtained within the past 90 days that shows no clinically significant abnormality and if the patient exhibits no signs or symptoms suggestive of pulmonary disease that would exclude the patient, then an additional chest X-ray is not required.

A chest computed tomography (CT) scan is to be completed only if indicated and at the discretion of the investigator.

4.5.3.4 Physical Examinations

A complete baseline physical examination will be performed at screening and should include an evaluation of the head, eyes, ears, nose, and throat and of the cardiovascular, dermatologic, musculoskeletal, respiratory, gastrointestinal, genitourinary, and neurologic systems. Any abnormality identified at baseline should be recorded on the General Medical History and Baseline Conditions eCRF.

At subsequent visits, limited, symptom-directed physical examinations should be performed. Changes from baseline abnormalities should be recorded in patient notes. New or worsened abnormalities should be recorded as AEs on the Adverse Event eCRF.

4.5.3.5 Laboratory Assessments

The following laboratory tests will be recorded at the time points indicated in the schedule of assessments (see [Appendix 1](#)). Whenever possible, laboratory samples should be drawn in the morning. Unscheduled laboratory assessments for safety issues are permitted at any time.

With the exception of samples for rituximab and HACA levels (for PK/PD assessments) obtained according to the schedule of assessments, all laboratory assessments requiring a blood sample are to be performed as part of routine clinical care.

The total volume of blood loss for laboratory assessments (including all safety, efficacy, PK/PD, and immunologic assessments) does not exceed the per-visit and per-cumulative visit recommendations made by the University of Pittsburgh's Institutional Review Board (IRB) and the NIH for the expected average weights of the patient. However, if the enrolled patient weighs < 13 kg, please check with the Roche Medical Monitor for planning the blood draws. This weight is based on acceptable blood draw limits of 2 mL/kg (blood draw in a day) or 4 mL/kg (blood draw in a month) at Children's Hospital Seattle.

The procedures for the collection, handling, and shipping of laboratory samples are specified in the Sample Handling and Logistics Manual supplied to sites.

The samples for this study should be classified, packed, and shipped as UN3373 Biological Substance, Category B.

Local Laboratory Assessments

Samples for the following laboratory tests will be sent to the study site's local laboratory for analysis:

- Serum ANCA sample: ANCA testing performed at the screening visit may be performed locally or centrally. All other ANCA testing should be performed centrally.
- Acute-phase reactants: erythrocyte sedimentation rate and C-reactive protein
- Urinalysis: dipstick for blood, protein, and glucose, and albumin to creatinine ratio
- Pregnancy test: urine dipstick test for all females of childbearing potential

Central Laboratory Assessments

Samples for the following laboratory tests will be sent to one or several central laboratories or to the Sponsor for analysis. Instruction manuals and supply kits will be provided for all central laboratory assessments.

- Serum ANCA sample: ANCA testing performed at the screening visit may be performed locally or centrally. All other ANCA testing should be performed centrally.
- Hematology or complete blood count: hemoglobin, hematocrit, red blood cells and indices (mean corpuscular volume, mean cell hemoglobin, mean corpuscular hemoglobin concentration), white blood cells, absolute differential, and platelet counts
- Serum chemistry: AST/SGOT, ALT/SGPT, alkaline phosphatase, total protein, total bilirubin (direct and indirect will be performed if total bilirubin is greater than the ULN), urea, uric acid, creatinine, potassium, sodium, chloride, calcium, phosphate, and glycosylated hemoglobin (HbA_{1c}).
- Urinalysis: microscopic examination if abnormal and applicable
- Pregnancy test: A serum pregnancy test will be performed at screening for all females of childbearing potential
- Hepatitis serology: HBcAb, HBsAg, and hepatitis C antibody (HCV Ab) at screening only or if clinically indicated during the trial

4.5.3.6 Immunologic Assessments

Determination of B- and T-cell populations will be performed by fluorescence-activated cell sorter (FACS) analysis, including, but not limited to, CD3, CD4, CD8, CD16/56, CD19, CD27, CD4/45RA/45RO, and CD8/45RA/45RO. In addition, quantitative immunoglobulin levels (including total immunoglobulin, immunoglobulin A [IgA], IgG, and IgM isotype levels).

4.5.4 Pharmacokinetic Assessments

During the remission induction phase of the study, each patient will provide serum samples for PK analysis (rituximab levels) prior to the first, second, third, and fourth doses; after completion of the first and fourth infusions; and subsequently on Days 29 (Month 1), 60 (Month 2), 120 (Month 4), and 180 (Month 6). The post-infusion PK sample should be taken from the opposite arm to that into which the rituximab infusion was administered.

4.5.5 Pharmacodynamic Assessments

[REDACTED]

[REDACTED]

[REDACTED]

[REDACTED]

[REDACTED]

4.5.6 Timing of Study Assessments

4.5.6.1 Screening and Pretreatment Assessments

Written informed consent for participation in the study must be obtained before performing any study-specific screening tests or evaluations. It will be obtained from parents or patient's legal guardian, with assent as appropriate by the patient, depending on the patient's level of understanding. Informed Consent Forms for enrolled patients and for patients who are not subsequently enrolled will be maintained at the study site.

Screening tests and evaluations will be performed at the screening visit and should be completed within 28 days of the baseline visit. Results of standard of care tests or examinations performed prior to obtaining informed consent and within 14 days prior to the screening visit may be used and do not need to be repeated for screening, at the discretion of the investigator. All screening evaluations must be completed and reviewed to confirm that patients meet all eligibility criteria before study enrollment. Please see [Appendix 1](#) for the schedule of screening assessments.

For entry into this study, patients will be screened for tuberculosis according to local/national guidelines. Results of screening tests will be reported on the eCRF.

The investigator will maintain a screening log to record details of all patients screened.

Patients who fulfill all the inclusion criteria and meet none of the exclusion criteria will be accepted into the study. The investigator or designated person will inform the IxRS and the patient will be allocated a patient number.

Any new information arising during the study that may affect the willingness of the patient to continue in the trial will be provided to the investigator and the patient as soon

as possible. Any changes to the protocol procedures will be subject to additional explanation and reconfirmation of consent to continue participation in the study.

4.5.6.1.1 Retesting for Laboratory Inclusion and Exclusion Criteria

If a patient does not meet laboratory criteria for a third time, he or she will be considered a screen failure.

It will not be considered retesting if blood samples have to be redrawn because of sample handling problems, breakage, or sample integrity.

4.5.6.1.2 Rescreening

At the discretion of the Sponsor and the investigator, a patient may be rescreened.

Rescreening refers to repeating the whole screening process. Rescreening is required if a patient has not met all the eligibility criteria within 28 days of the original screening visit.

Patients are only permitted to be rescreened once. Each patient must be reconsented before rescreening occurs.

It will not be considered rescreening if blood samples have to be redrawn because of sample handling problems, breakage, or sample integrity. *In the case of a protocol amendment, potential patients may be reassessed for eligibility according to any updated inclusion and exclusion criteria.*

4.5.6.2 Baseline Assessments (Day 1) and Remission Induction Phase

Patients must receive three doses of methylprednisolone at 30 mg/kg/day (up to 1 g/day) or the equivalent dose of other glucocorticoids by IV infusion, which can occur at any time, up to and including Day 1. If clinically indicated, and at the discretion of the investigator, additional daily doses (up to three) of methylprednisolone (30 mg/kg, up to 1 g/day) can be given by IV infusion. No more than six doses in total may be given. All doses of methylprednisolone must be completed prior to the first rituximab infusion.

The first rituximab infusion (baseline visit) must occur no longer than 14 days after the final IV glucocorticoid dose; the final IV glucocorticoid dose may be given on Day 1 (prior to the first rituximab infusion).

All assessments must be performed on the day of the specified visit, unless a time window is specified in the schedule of assessments (see [Appendix 2](#)). Assessments scheduled on the day of study treatment administration should be performed prior to administration of study treatment, unless otherwise noted in the schedule of assessments. PRO assessments should be performed prior to the completion of other study assessments.

Please see [Appendix 1](#) for the schedule of assessments performed during the treatment period.

4.5.6.3 Follow-Up Visits

Following the remission induction phase, which ends at Month 6, patients will be followed up for a minimum of 12 months at visits conducted every 3 months. Patients who are protocol remission failures or who experience disease flare that cannot be controlled by glucocorticoids alone should receive treatment according to local standard of care, at the discretion of the investigator and will remain in the study (see Section [4.4.2.1](#)). After Month 18, patients will be followed at study visits every 3 months until the common closeout date. The procedures performed at the follow-up visits will be similar to those performed at the Month 18 visit. The schedule of assessments for the follow-up phase is provided in [Appendix 1](#).

4.5.6.4 Extended Follow-Up Visits

At the common closeout date, patients whose *peripheral* B cells remain depleted, will continue to attend study visits every 3 months until their *peripheral* B-cell counts have returned to *pre-rituximab* baseline levels or to within the normal range for the population, whichever is lower. *Safety, (adverse events), central laboratory and immunologic parameters, including immunoglobulins, will continue to be assessed in extended safety follow-up (see Appendix 1)*. If a patient receives any B cell–depleting therapy (*commercial or investigational*) or any other agent that affects the return of B cells, including, but not limited to, rituximab, CYC and AZA, on or after the common closeout date, he or she will not be followed any further (although routine clinical follow-up after the end of the study will continue, according to local practice).

4.5.7 Early Withdrawal Visit

Patients who discontinue from the study early because of non-compliance or withdrawal of consent will be asked to return to the clinic to attend an early withdrawal visit and will be encouraged to enter follow up.

If the investigator judges that continuing rituximab is no longer in the participant's best interest, the participant will be asked to complete a withdrawal visit and will remain in the study *for follow-up (see Section 3.1.8)*. *From the point of withdrawal, a patient may no longer receive rituximab as part of this protocol*. A schedule of assessments for the withdrawal visit is provided in [Appendix 1](#).

4.5.8 Unscheduled Visits

Patients may attend the clinic for unscheduled visits at any time for additional safety monitoring or disease surveillance at the discretion of the investigator. If a patient has an unscheduled visit during the study that falls outside of a scheduled visit window, assessments will be performed at the discretion of the investigator. If a patient has an unscheduled visit within a scheduled visit window, it is at the discretion of the investigator to perform the scheduled assessments indicated for the scheduled visit.

4.5.9 Progressive Disease Before Remission

Progressive disease before remission by PVAS is defined as:

1. Persistence or worsening of a major PVAS item present at entry, and/or
2. A new major PVAS item that is not present at entry

Major (and minor) PVAS items are defined in [Table 2](#).

Progressive disease before remission by BVAS/WG is defined as:

1. Persistence or worsening of a major BVAS/WG item present at entry, and/or
2. A new major BVAS/WG item that is not present at entry

Major (and minor) BVAS/WG items are defined in [Table 3](#).

Patients with progressive disease before remission by Month 6 will receive additional treatment as per local standard of care and will be considered a 'treatment failure' however, data collection should continue within the trial.

4.6 PATIENT, STUDY, AND SITE DISCONTINUATION

4.6.1 Patient Discontinuation

Patients may withdraw early from the study for the following reasons:

- Withdrawal of informed consent
- Loss to follow-up
- Death

Parents or guardians have the right to withdraw their child from the study at any time for any reason. In the case that a patient prematurely discontinues from the study, the parents/guardians should be asked whether they can be contacted for further information. The outcome of that discussion should be documented in both the medical records and on the eCRF. If the patient is lost to follow-up, the investigator should contact the patient's parents/guardian or a responsible relative by telephone followed by registered mail or through a personal visit to establish as completely as possible the reason for the withdrawal. A complete final evaluation at the time of the patient's withdrawal should be made with an explanation as to why the patient is withdrawing from the study.

4.6.2 Criteria for Premature Study Drug Termination or Study Withdrawal by Investigator or Sponsor

The investigator and Sponsor have the right to discontinue a patient from study drug or withdraw a patient from the study at any time. Reasons for discontinuation of study drug or withdrawal from the study may include, but are not limited to, the following:

- Non-compliance with the requirements of the study

- Any AE that in the opinion of the investigator or the Sponsor precludes further study participation
- The best interest of the patient

When applicable, parents/guardians should be informed of circumstances under which their child's participation may be terminated by the investigator without the parent's/guardian's consent. The investigator may withdraw patients from the study in the event of intercurrent illness, AE, treatment failure after a prescribed procedure, lack of compliance with the study and/or study procedures (e.g., dosing instructions, study visits), cure, or any reason where it is felt by the investigator that it is in the best interest of the patient to be discontinued from the study. Any administrative or other reasons for withdrawal must be documented and explained to the patient.

All patients who permanently discontinue infusions of rituximab but have not terminated study participation (withdrawn consent or have been withdrawn by the investigator or Sponsor according to the above examples) will have safety evaluations, including all withdrawal visits, as shown in the schedule of assessments (see [Appendix 1](#)). If the reason for withdrawal of a patient from the study drug is an AE, the principal specific event will be recorded on the eCRF. If possible, the patient should not be withdrawn from the study but only from study drug and, if possible, should be followed until the AE has resolved (see Section [5.5.1](#)). An excessive rate of withdrawals can render the study non-interpretable; therefore, unnecessary withdrawal of patients should be avoided. Should a patient decide to withdraw, all efforts will be made to complete and report the observations prior to withdrawal as thoroughly as possible.

4.6.3 Documentation at Withdrawal from Study

Every effort should be made to obtain information about patients who withdraw from the study. The primary reason for withdrawal from the study should be documented on the appropriate eCRF. Patients who withdraw from the study will not be replaced.

4.6.4 Study and Site Discontinuation

The Sponsor has the right to terminate this study at any time. Reasons for terminating the study may include, but are not limited to, the following:

- The incidence or severity of AEs in this or other studies indicates a potential health hazard to patients.
- Patient enrollment is unsatisfactory.

The Sponsor will notify the investigator if the study is placed on hold, or if the Sponsor decides to discontinue the study or development program. The Sponsor has the right to replace a site at any time. Reasons for replacing a site may include, but are not limited to, the following:

- Excessively slow recruitment

- Poor protocol adherence
- Inaccurate or incomplete data recording
- Non-compliance with the International Conference on Harmonisation (ICH) guideline for Good Clinical Practice

5. ASSESSMENT OF SAFETY

5.1 SAFETY PARAMETERS AND DEFINITIONS

Safety assessments will consist of monitoring and recording of AEs, SAEs, and non-serious AEs of special interest; measurement of protocol-specified safety laboratory assessments; measurement of protocol-specified vital signs; and other protocol-specified tests that are deemed critical to the safety evaluation of the study.

Certain types of events require immediate reporting to the Sponsor, as outlined in Section 5.4.

5.2 CLINICAL ADVERSE EVENTS

According to the ICH guideline for Good Clinical Practice, an AE is any untoward medical occurrence in a clinical investigation subject administered a pharmaceutical product, regardless of causal attribution. An AE can therefore be any of the following:

- Any unfavorable and unintended sign (including an abnormal laboratory finding), symptom, or disease temporally associated with the use of a medicinal product, whether or not considered related to the medicinal product
- Any new disease or exacerbation of an existing disease (a worsening in the character, frequency, or severity of a known condition), except as described in Section 5.3.6.4
- Recurrence of an intermittent medical condition (e.g., headache) not present at baseline
- Any deterioration in a laboratory value or other clinical test (e.g., ECG, X-ray) that is associated with symptoms or leads to a change in study treatment or concomitant treatment or discontinuation from study drug
- AEs that are related to a protocol-mandated intervention, including those that occur prior to assignment of study treatment (e.g., invasive screening procedures such as biopsies)

AEs will be graded according to the National Cancer Institute Common Terminology Criteria for Adverse Events (NCI CTCAE), Version 4. AEs not listed in the NCI CTCAE will be graded using the following criteria:

- Grade 1: mild; asymptomatic or mild symptoms; clinical or diagnostic observations only; intervention not indicated
- Grade 2: moderate; minimal, local or non-invasive intervention indicated

- Grade 3: severe or medically significant but not immediately life threatening; hospitalization or prolongation of hospitalization indicated
- Grade 4: life-threatening consequences; urgent intervention indicated
- Grade 5: death related to an AE

5.2.1 Serious Adverse Events (Immediately Reportable to Roche)

An SAE is any AE that meets any of the following criteria:

- Is fatal (i.e., the AE actually causes or leads to death). (Note: Death is an outcome, not an event. The term “sudden death” should only be used when the cause is of a cardiac origin as per standard definition. The terms “death” and “sudden death” are clearly distinct and must not be used interchangeably.)
- Is life threatening (i.e., the AE, in the view of the investigator, places the patient at immediate risk of death)

This does not include any AE that had it occurred in a more severe form or was allowed to continue might have caused death.

- Requires in-patient hospitalization or prolongation of existing hospitalization (see Section 5.3.6.5)
- Results in persistent or significant disability/incapacity (i.e., the AE results in substantial disruption of the patient’s ability to conduct normal life functions)
- Is a congenital anomaly/birth defect in a neonate/infant born to a mother exposed to study drug
- Is a significant medical event in the investigator's judgment (e.g., may jeopardize the patient or may require medical/surgical intervention to prevent one of the outcomes listed above)

The terms “severe” and “serious” are not synonymous. Severity refers to the intensity of an AE (rated as mild, moderate, or severe, or according to NCI CTCAE criteria; see Section 5.3.3); the event itself may be of relatively minor medical significance (such as severe headache without any further findings).

Severity and seriousness need to be independently assessed for each AE recorded on the eCRF.

SAEs are required to be reported by the investigator to the Sponsor within 24 hours after learning of the event (see Section 5.4.2 for reporting instructions).

5.2.2 Relationship to Study Drug

The relationship of the AE or SAE to the rituximab study treatment must be assessed by the investigator or his or her designee.

5.2.3 Management of Specific Adverse Events

Adherence to the planned dosing schedule with rituximab infusions is required unless an adjustment is necessary for safety reasons. The following risk mitigation and dose modification rules apply. Recommendations for vigilance with signs and symptoms of particular safety events of interest are summarized in the following sections. During study visits when the rituximab infusion is interrupted for toxicity, all other study assessments should be performed as per the schedule of assessments (see [Appendix 1](#)).

5.2.3.1 Infusion-Related Reactions following Rituximab Administration

Rituximab is associated with IRRs, including, but not limited to, headache, pruritus, throat irritation, flushing, rash, urticaria, hypertension, hypotension, and pyrexia, which may be related to release of cytokines and/or other chemical mediators. Participants will receive at least three doses of IV methylprednisolone, followed by oral prednisolone or prednisone (see Section [4.3.2.1.3](#)). IV glucocorticoids may help prevent severe infusion reactions potentially associated with rituximab. Medication, consisting of an analgesic/anti-pyretic drug and an anti-histaminic drug, should always be administered prior to each infusion of rituximab (see Section [4.3.2.1.3](#)). Healthcare professionals administering the rituximab infusions must be trained in the appropriate administrative procedures and be able to recognize the symptoms associated with potential anaphylactic or hypersensitivity reactions.

For patients with RA, GPA, and MPA, most infusion-related events reported in clinical trials were mild to moderate in severity. Severe IRRs with fatal outcome have been reported in the postmarketing setting in RA patients. Patients with pre-existing cardiac conditions and those who experienced prior cardiopulmonary adverse reactions must be closely monitored. In general, the proportion of patients experiencing any infusion reaction was higher following the first infusion of any treatment course than following the second infusion. Subsequent rituximab infusions were better tolerated by patients than the initial infusion. Less than 1% of patients experienced serious IRRs, with most of the events reported during the first rituximab infusion. The reactions reported were usually reversible with a reduction in rate or interruption of the infusion and with administration of an anti-pyretic medication, an antihistamine, and occasionally oxygen, IV saline, bronchodilators, or glucocorticoids, as required. Depending on the severity of the IRR and the required interventions, treatment with rituximab should be temporarily or permanently discontinued. In most cases, the infusion can be resumed at a 50% reduction in rate when symptoms have completely resolved.

Anaphylactic and other hypersensitivity reactions have been reported following the IV administration of proteins to patients. Medicinal products for the treatment of hypersensitivity reactions (e.g., epinephrine, antihistamines, and glucocorticoids) must be available for immediate use in the event of an allergic reaction during administration of rituximab. If a patient has symptoms of anaphylaxis or serious hypersensitivity, or

requires an interruption of the study drug because of symptoms of anaphylaxis or hypersensitivity, administration of rituximab must be discontinued permanently. Patients will be asked to complete a withdrawal visit but will remain in the study (see Section 3.1.8). A schedule of assessments for the withdrawal visit is provided in Appendix 1.

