Although rituximab may be administered on an outpatient basis, patients may be hospitalized for observation at the discretion of the investigator. Irrespective, rituximab should be administered in a hospital or clinic environment where full resuscitation facilities are immediately available, along with qualified resuscitative personnel and under close supervision of the investigator or designee.

Dosage

The dose of rituximab will be calculated by the physician on the basis of 375 mg/m² of body weight (no maximum dose).

Preparation

Use appropriate aseptic technique. Dilute rituximab to a final concentration of 1 mg/mL to 4 mg/mL in 0.9% NaCl, or 5% Dextrose in Water (USP or British Pharmacopoeia) to a final concentration 1 mg/mL to 4 mg/mL. Gently invert the bag to mix the solution. Do not mix or dilute with other drugs. Discard any unused portion left in the vial. Parenteral drug products should be inspected visually for particulate matter and discoloration prior to administration. No incompatibilities between rituximab and polyvinylchloride or polyethylene bags have been observed.

FOR ALL TREATMENT COURSES THE INFUSION RATES FOR THE FIRST AND SUBSEQUENT INFUSION MUST BE ADHERED TO AS FOLLOWS:

Patients should be medicated pre-infusion with paracetamol/acetaminophen and cetirizine hydrochloride (or similar antihistamine), both according to labelled age-related doses, to be given 1 hour (\pm 15 minutes) before each infusion of rituximab.

First Infusion

Rituximab infusions should commence at a rate of 25 mg/h. This may be escalated at a rate of 25 mg/h increments every 30 minutes to a maximum of 200 mg/h. An example of an infusion schedule is presented below.

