Appendix 7 Procedures for the Intravenous Administration of Rituximab (cont.)

Final Concentration = 1 – 4 mg/mL		
Infusion Rate		Minutes
mg/h ^a	mL/h ^a	
25	(.....)	30
50	(.....)	30
75	(.....)	30
100	(.....)	30
125	(.....)	30
150	(.....)	30
175	(.....)	30
200	(.....)	thereafter

^a For countries not able to set the infusion pump to an accuracy of 0.5 mL/h, the rate is to be rounded down to the nearest whole number.

Subsequent Infusions

Patients who have tolerated the first infusion of rituximab well may receive the second infusion. Infusion schedule described for the first infusion should be used also for all subsequent infusions; the infusion rate can be adjusted if the first infusion was well tolerated. Subject to investigator's discretion, corticosteroid premedication with an IV infusion of 100 mg of methylprednisolone may be administered at least 30 minutes prior to the infusion of rituximab (but not prior to clinical assessments) if the patient has experienced an infusion-related reaction with a previous rituximab infusion.

In the event of the patient experiencing an infusion-related reaction during first or any subsequent infusions, the infusion should be stopped immediately. The patient should be clinically assessed and appropriate treatment should be given as per local policy. The principle investigator or sub-investigator(s) should also be informed as soon as possible and all adverse events should be reported as required in Section 5.2. Once the adverse event has resolved, infusion can be restarted at the previous tolerated rate and should be given at the previous reduced rate for 30 minutes. If tolerated, the rate may be increased to the next closest rate on the patient's infusion schedule. Further information is provided in Section 5.2.3.1.

All rituximab infusions should be made through a dedicated line. After the end of each infusion, the IV line should remain in situ for at least 1 hour in order to be able to administer drugs intravenously if necessary. If there are no adverse events during this period of time, the IV line may be removed.

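### Section 5.2.3.1 and Appendix 7 give different restart rates after an infusion reaction, and the protocol does not say which governs

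*Protocol*

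**What the plan says.** **Restart rate.** Protocol Section 5.2.3 introduces its content with the words "The following risk mitigation and dose modification rules apply". Within it, Section 5.2.3.1 states: "In most cases, the infusion can be resumed at a 50% reduction in rate when symptoms have completely resolved". Appendix 7 says that on a reaction "the infusion should be stopped immediately". Once the event has resolved, the "infusion can be restarted at the previous tolerated rate and should be given at the previous reduced rate for 30 minutes", and then: "If tolerated, the rate may be increased to the next closest rate on the patient's infusion schedule". Section 5.2.3.1 has no rule for raising the rate again.

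**When restart is not allowed.** Section 5.2.3.1 adds that if a patient "requires an interruption of the study drug because of symptoms of anaphylaxis or hypersensitivity, administration of rituximab must be discontinued permanently". The restart paragraph of Appendix 7 does not repeat this. It closes by sending the reader to Section 5.2.3.1 for further information.

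**Whether rates are fixed.** Appendix 7 states in capitals: "FOR ALL TREATMENT COURSES THE INFUSION RATES FOR THE FIRST AND SUBSEQUENT INFUSION MUST BE ADHERED TO AS FOLLOWS". Under Subsequent Infusions it applies the first-infusion schedule to all later infusions, and in the same sentence says that "the infusion rate can be adjusted if the first infusion was well tolerated". It gives no alternative schedule and no extent for the adjustment.

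**SAP.** Section 6 and output AE002.2SP define an infusion-related reaction by its timing relative to the infusion and by event-term group, and count several symptoms at one infusion as one reaction. Outputs EX001SP and EX002SP report interrupted or modified infusions separately.

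**The concern.** Staff treating a child who has just reacted find one restart rate in the body of the protocol and another in the administration procedure. Both are current text, and a site following either can claim compliance.

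The routes into the two texts differ. Sections 4.3.2.1.5 and 4.4.4 send readers to Section 5.2.3 for dosage modification and interruption. Section 4.3.2.1.4 sends readers to Appendix 7 for more on monitoring during infusion. The text a site acts on may depend on where its staff started reading.

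The stop rule adds to the difficulty. Section 5.2.3.1 lists rash, urticaria and pruritus among infusion-related reactions, and these can also be read as signs of hypersensitivity. Appendix 7 stops the infusion for every reaction. Staff must then decide whether that interruption was for hypersensitivity, and the page they are working from does not mention that this decides whether a restart is open at all.

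Safety and tolerability form a primary objective, so uniform handling of reactions matters for the patients first and for the exposure summaries second.

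**Working it through.** The plan gives no figure on this point, so there is none to reproduce. The check compares the two restart instructions at each step of the Appendix 7 schedule.

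**Inputs**
- Section 5.2.3.1: restart at half the rate.
- Appendix 7: restart at the previous tolerated rate.
- Appendix 7, First Infusion: start at 25 mg/h and rise by 25 mg/h every 30 minutes to at most 200 mg/h. The table of steps is offered as an example of a schedule.
- Assumption: the previous tolerated rate is the step immediately below the one at which the reaction occurred. The protocol does not define it.

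**Formulas**, with r the rate at the reaction in mg/h:
- Section 5.2.3.1 rate = 0.5 × r
- Appendix 7 rate = r − 25
- Ratio, Appendix 7 to Section 5.2.3.1 = (r − 25) / (0.5 × r)

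| r | 0.5 × r | r − 25 | Ratio |
|---|---|---|---|
| 25 | 12.5 | no earlier step | – |
| 50 | 25 | 25 | 1.00 |
| 75 | 37.5 | 50 | 1.33 |
| 100 | 50 | 75 | 1.50 |
| 125 | 62.5 | 100 | 1.60 |
| 150 | 75 | 125 | 1.67 |
| 175 | 87.5 | 150 | 1.71 |
| 200 | 100 | 175 | 1.75 |

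**Results**
- The two texts coincide only at 50 mg/h, and the gap widens as the rate rises.
- At 25 mg/h, halving gives a rate below the schedule and Appendix 7 gives none.
- At 25, 75, 125 and 175 mg/h, the halved rate is not a step on the schedule.

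**Cross-references.** Appendix 7 cites Section 5.2.3.1. Section 5.2.3.1 cites Sections 4.3.2.1.3 and 3.1.8 and Appendix 1, but not Appendix 7. The link runs one way, and no sentence ranks the two texts.

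**Consequence for the SAP outputs.** The restart rule acts only after a reaction has begun. Because several symptoms at one infusion count as one reaction, a patient restarted at either rate is already counted at that infusion in AE002.2SP. EX001SP is more exposed: neither document says whether a rate adjustment that Appendix 7 permits counts as a modified infusion. With 25 patients starting an infusion, each one classified differently moves that percentage by 1/25 = 4 points.

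**The case against.** The strongest reply is that these are permissive and partly undefined sentences, not two fixed rates. Section 5.2.3.1 speaks of most cases and of what can be done, and Appendix 7 also says *can*. The Appendix 7 sentence mentions a reduced rate, which could be read as the halved rate of the section it later cites. This stands in part: the figures above depend on a reading that the protocol does not supply. It does not remove the problem, because a reader who needs a rate still finds two descriptions, and Appendix 7 names two rates in one sentence without defining either.

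Four stronger readings are tempting, and the documents do not support them.

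- **That the two sections cite each other, so that neither can govern.** Only Appendix 7 cites the other, and Section 5.2.3 presents its content as rules. The accurate statement is that precedence is never stated.
- **That Appendix 7 permits a restart after every kind of reaction, against the permanent-stop rule.** The word *any* there qualifies infusions, not reactions. A general permission that points to the section holding a specific prohibition is not a flat contradiction. What remains is an omission at the point of use.
- **That adjustment of later infusions is unlimited.** It is conditional on the first infusion having been well tolerated. The schedule carried forward has a 200 mg/h maximum, and push or bolus administration is excluded. The gap is that the extent of adjustment is unstated beside a heading that makes the rates mandatory.
- **That the restart conflict distorts the infusion-reaction counts.** The one-reaction-per-infusion rule prevents this for the patient count at that infusion.

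**Conclusion.** The inconsistency is real and should be corrected. Sections 5.2.3.1 and Appendix 7 describe the restart rate differently, and nothing says which prevails. Under the one-step assumption they differ at every step where both give a rate except 50 mg/h, with Appendix 7 at 1.33 to 1.75 times the Section 5.2.3.1 rate from 75 to 200 mg/h. Under another reading of the undefined terms the size would change.

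Two lesser defects go with it: mandatory rates beside an adjustment of unstated extent, and a restart paragraph that is silent on the permanent-stop rule.

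The case for acting is consistent care of children who react. The documents do not quantify a safety effect, and none is claimed here. The study is single-arm and descriptive, and any effect on the data is mainly in the interrupted or modified infusion summaries. This does not put the primary analyses in doubt.

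**What to change.** The sponsor should reconcile Section 5.2.3.1 with Appendix 7 so that the protocol contains:

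1. one instruction for restarting after a reaction, with every rate it names defined, including what applies at the lowest step;
2. one statement of when restart is not allowed, repeated or explicitly cited in the Appendix 7 restart paragraph;
3. one statement of whether, and how far, later infusions may depart from the schedule;
4. a sentence saying which section governs.

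The SAP should add a line to EX001SP and EX002SP saying whether a permitted rate adjustment counts as a modification. The choice of rate and rule belongs to the sponsor and its clinical advisers.

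The cost is a correction to the protocol text and one clarifying line in the SAP. Sample size, endpoints and analyses do not change.
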